5.2.6.2 Adverse event collection and reporting

5.2.6.2.1 AE Collection

The investigator shall maintain and keep detailed records of all AEs in the patient files. The following must be collected and documented on the appropriate CRF(s) by the investigator (special notes on SAE form reporting where needed):

- From the time of first dose of trial drug administration in the extension trial until the individual patient's end of trial:
all AEs (serious and non-serious) and all AESIs.
- All AEs that started in the parent trial (onset date in parent trial) and are still ongoing after 1st IMP administration in the extension trial:
 - Re-record the AE in the extension trial eCRF with the same information as it was recorded in the parent trial.
 - Should the AE end during the course of the extension trial,
⇒ update both - the extension trial eCRF and the parent trial eCRF. If the parent trial is already locked, update only the extension trial eCRF. In this case the

update for the parent trial will be handled outside of the eCRF of the parent trial.

- However, concerning reporting on the SAE form (if applicable), the follow-up report will still be sent on the parent trial SAE form, no new SAE form is to be completed for the extension trial.
- If the intensity of an ongoing AE changes after 1st IMP administration in the extension trial:
 - ⇒ update both - the extension trial eCRF and the parent trial eCRF- with the end date for the initial/previous intensity. If the parent trial is already locked, update only the extension trial eCRF. In this case the update for the parent trial will be handled outside of the eCRF of the parent trial.
 - ⇒ The AE with the new intensity will be handled as new event; this means it is only recorded in the extension trial eCRF.
 - Example: If the intensity increased then the new AE name/term should contain “Worsening of...” or “Exacerbation of...”

Considerations for reporting on the SAE form, when intensity change qualifies as worsening/exacerbation of an event that had already been reported on the SAE form:

- corresponding follow up report to be sent on the parent trial SAE form with date of worsening as event end date.
- extension trial SAE form to be sent as initial report for the extension trial for new event “Worsening/Exacerbation of....” with date of worsening as onset date.

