7.2.2 Primary endpoint analyses

Refer to [Section 2.1.2](#) for the description of the primary endpoint. The primary analyses will be descriptive in nature. All treated patients will be included in the primary analyses. No hypothesis testing is planned.

Adverse events will be coded using the Medical Dictionary for Drug Regulatory Activities (MedDRA). Standard BI summary tables and listings will be produced. All adverse events with an onset between start of treatment of this trial and end of the residual effect period

(REP), a period of 16 weeks after the last dose of trial medication, will be assigned to the on-treatment period for evaluation.

Adverse events that start before first drug intake and deteriorate under treatment will also be considered as 'treatment-emergent'. For all patients who, due to a fistula relapse received the intensified treatment with spesolimab, safety assessments including adverse events, laboratories, vital signs, etc., which occurred subsequent to such intake will be excluded from presentations according to the planned treatment; these data will, however, be included in summaries where all data after any use of spesolimab are displayed.

Exposure-adjusted adverse event incidence rates will be calculated using the following approach:

The incidence rate (per 100 patient years) of a selected adverse event (also known as the incidence density rate or person-time incidence rate) is defined as the number of patients experiencing the adverse event during the time at risk divided by the total time of patients at risk to contribute an event to the analysis multiplied by 100, where:

$$\text{Time at risk (in subject years)} = ((\text{date of onset of AE} - \text{study drug start date}) + 1) / 365.25$$

The study drug start date refers to the start date of this trial. If, for a patient, no treatment emergent adverse event occurred, then the time at risk will be censored at the minimum of: date of death; drug stop date + 112 days; start date of CD inflammatory flare or fistula relapse treatment with spesolimab; last contact date; or, date of database snapshot if an interim analysis was performed.

For each AE, the incidence rate will therefore be calculated as:

$$\text{Incidence rate} = 100 * \text{number of patients with TEAE} / \text{Total TEAE-specific time at risk.}$$

Exact 95% confidence intervals around the observed AE incidence rate will also be provided.

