7.2.5 Safety analyses

Refer to [Section 7.2.2](#) for a description of the analyses of the primary endpoint, which for the present trial is a safety endpoint.

For the additional safety analyses described below, all treated patients will be included. In general, these additional safety analyses will be descriptive in nature and will be based on BI standards. No hypothesis testing is planned.

Statistical analysis and reporting of adverse events will concentrate on treatment-emergent adverse events, i.e. all adverse events occurring between start of treatment in this trial and the end of the REP. Refer to [Section 7.2.2](#) for the complete description of a treatment-emergent adverse event.

Frequency, severity, and causal relationship of adverse events will be tabulated by system organ class and preferred term after coding according to the current version of the Medical Dictionary for Drug Regulatory Activities (MedDRA) at database lock.

Laboratory data will be analysed both quantitatively as well as qualitatively. The latter will be done via comparison of laboratory data to their reference ranges. Values outside the reference range as well as values defined as clinically relevant will be summarised.

Laboratory data will be analysed descriptively with regard to distribution parameters as well as with regard to frequency and percentage of patients with abnormal values or clinically relevant abnormal values.

Vital signs, physical examinations, or other safety-relevant data observed at screening, baseline, during the course of the trial and at the end-of-trial evaluation will be assessed with regard to possible changes compared to findings before start of treatment.

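### A parent-trial AE that only eases opens a new event record, and the visible treatment-emergent rule has no exception to keep it out of the primary rate

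*Protocol*

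**What the plan says.** **Recording (CTP 5.2.6.2.1).** An AE that began in the parent trial and is still ongoing after the first extension dose is re-recorded in the extension eCRF with its parent-trial information. A further step applies "If the intensity of an ongoing AE changes after 1st IMP administration in the extension trial". The existing record is then updated "with the end date for the initial/previous intensity", and "The AE with the new intensity will be handled as new event; this means it is only recorded in the extension trial eCRF". The naming convention for worsening is only an illustration: "Example: If the intensity increased then the new AE name/term should contain" a worsening or exacerbation prefix. The SAE-form instructions for a worsening report the new event "with date of worsening as onset date". No onset date is stated for a record opened by a decrease. CTP 8.3.1 makes an onset date mandatory for every AE.

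**Classification.** CTP 7.2.2 places on treatment "All adverse events with an onset between start of treatment of this trial and end of the residual effect period". It then adds: "Adverse events that start before first drug intake and deteriorate under treatment will also be considered" treatment-emergent. CTP 7.2.5 describes treatment-emergent events as "all adverse events occurring between start of treatment in this trial and the end of the REP" and refers to CTP 7.2.2 for the full definition. SAP 7.8.1 assigns every AE to an analysis period, works from the AE start date, and refers to CTP 7.2.2 for the rate calculation.

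**Rate.** CTP 7.2.2 divides the number of patients with a TEAE by total time at risk. A patient's time at risk stops at the onset of the AE.

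**The concern.** The recording rule is triggered by any change in intensity, while the classification rule looks only at when a record starts. Nothing visible connects the two for a decrease. A patient whose parent-trial AE is getting better could therefore enter the numerator of the primary any-TEAE rate and stop contributing person-time. Rates by preferred term could move in the same way.

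This does not fit the evident purpose of the deterioration sentence in CTP 7.2.2, which brings in AEs present before treatment when they get worse. Every patient arrives from a parent trial, so carried-over AEs are a built-in feature of the design. The primary result is this descriptive rate, in at most about 20 patients.

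**Working it through.** **Rule trace.** Take, as an assumed example, a parent-trial AE that is grade 3 at the first extension dose and falls to grade 2 on day 30.

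| Record | Onset | Status under the visible rules |
|---|---|---|
| Grade 3, re-recorded | In the parent trial | Started before first dose and did not deteriorate: not treatment-emergent |
| Grade 2, new event, onset = date of change | Day 30 | Onset on treatment: treatment-emergent; time at risk ends at 30/365.25 = 0.08 y if it is the patient's first TEAE |
| Grade 2, new event, parent-trial onset kept | In the parent trial | Not caught by the onset rule: no effect |

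The second row is the natural reading. The old record is closed at the change, the new one is called a new event, an onset date is required, and the only stated analogue uses the date of change. It remains an inference.

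**Who is exposed.** CTP 5.2.6.2.1.5 grades AEs 1 to 4 under its intensity section (5.2.6.1.5). A grade 1 AE cannot ease; it can only end. The overall rate changes only for a patient with a grade 2 or higher AE ongoing at roll-over that eases without resolving before any genuine TEAE.

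**Direction.** If a genuine TEAE came first, nothing changes. Otherwise person-time falls and the event count stays the same or rises by one. The rate goes up or does not move.

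**Illustrative size.** The plan gives no expected rate, so there is no figure to reproduce. From the documents: up to 20 patients (CTP 7.5) and the rate formula (CTP 7.2.2). Assumed: follow-up F = 1.5 y, constant first-TEAE hazard L per year, easing at time t, and k eased patients.

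- Uneased patient: expected events p = 1 − exp(−L·F); expected time p/L.
- Eased patient: 1 event; expected time (1 − exp(−L·t))/L. This averages over whether a genuine TEAE comes first.
- Rate per 100 PY = 100 × [(20 − k)p + k] / [(20 − k)p/L + k(1 − exp(−L·t))/L].

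For L = 2/3, t = 0.1, k = 1: p = 0.632, numerator 19 × 0.632 + 1 = 13.01, denominator 19 × 0.948 + 0.097 = 18.11, rate 71.8.

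| L (per year) | t (y) | Rate, k = 0 | Rate, k = 1 | Change |
|---|---|---|---|---|
| 2/3 | 0.1 | 66.7 | 71.8 | +7.7% |
| 2/3 | 0.5 | 66.7 | 70.6 | +5.8% |
| 3 | 0.1 | 300.0 | 311.7 | +3.9% |
| 3 | 0.5 | 300.0 | 303.4 | +1.1% |

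The chance that the easing comes before any genuine TEAE is exp(−L·t): 0.94 in the first row and 0.22 in the last.

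**Single-patient extremes with fixed times.** Assume 12 first TEAEs at 0.5 y and 8 patients TEAE-free to 1.5 y. Person-time is 12 × 0.5 + 8 × 1.5 = 18.0, so the rate is 12/18.0 = 66.7 per 100 PY, exact Poisson 95% CI 34.4 to 116.5.

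- Genuine TEAE came first: no change.
- Easing at 0.1 y precedes a genuine TEAE at 0.5 y: 12/(18.0 − 0.4) = 12/17.6 = 68.2 (+2.3%).
- Easing at 0.1 y in an otherwise TEAE-free patient: 13/(18.0 − 1.4) = 13/16.6 = 78.3 (+17.5%).

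**One preferred term with no genuine case.** The rate goes from 0/30.0 = 0 to 1/(19 × 1.5 + 0.1) = 1/28.6 = 3.5 per 100 PY.

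**The case against.** **The onset date is inferred.** Date of change as onset is stated only for worsening, and only on the SAE form. If the parent-trial onset is kept, there is no inflation. This stands, and it makes the point conditional. Against it, keeping the old onset would give a new event that overlaps the record it replaces.

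**The deterioration sentence points the other way.** If every intensity change already produced an on-treatment onset, worsening AEs would be caught by the onset rule and the sentence would add almost nothing. It does more work if parent-trial AEs are judged by their original start and count only on worsening. CTP 7.2.5 defers to CTP 7.2.2, so its shorter wording is not independent support. This is fair evidence of intent. But the sentence says such events are *also* treatment-emergent: it adds cases and removes none. A reader might infer that it contradicts the onset rule; it does not.

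**Relevant text is not visible.** SAP 7.8.1 relies on a company AE standard for summarisation and on SAP 5.4.1 for the intensity measure. Neither can be read here, and either may already deal with eased records. A reader might infer that the plan has no such rule anywhere; the documents support only that none is visible in the sections cited.

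**Few patients are exposed and no test is affected.** The exposed group is narrow, CTP 3.3.3 excludes patients with treatment-limiting AEs in induction, and the individual AE listings in SAP 7.8.1 may show a closed and reopened record. This stands and sets the priority. A listing would not, however, correct the tabulated rate.

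**Conclusion.** The point holds in conditional form. As visible, the recording rule and the onset rule together can count a pure improvement as a TEAE and end time at risk, which the deterioration sentence suggests was not intended. This rests on the new record's onset being the date of change, and on neither the company standard nor SAP 5.4.1 already handling it.

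The effect is upward or nil and may be zero, because the documents do not say how many parent-trial AEs eased. For one affected patient, the averaged illustration gives +1.1% to +7.7%, and the fixed-time extremes run from 0 to +17.5%. The values on the 66.7 background all lie inside its exact interval of 34.4 to 116.5. A reader might infer that the primary rate is in fact inflated, or that several patients are affected. Nothing in the documents supports either. The priority is low: the analysis is descriptive and no hypothesis is tested.

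**What to change.** Add one rule to SAP 7.8.1: a record created solely by a decrease in intensity of an AE with onset before the first extension dose is linked to that AE, is listed, is not treatment-emergent, and does not end time at risk. Worsening continues to count under CTP 7.2.2. The rule works whichever onset date the new record carries, so the collection instructions need not change.

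If the company AE standard or SAP 5.4.1 already says this, a one-line reference to it is enough.

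No protocol amendment or new data are needed. The SAP history table shows that version 2.0 was itself revised after the termination decision and before final database lock. The small cost is a linkage check on records already collected.

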5.2.6.2.2 AE reporting to the sponsor and timelines

The investigator must report SAEs, AESIs, and non-serious AEs which are relevant for the reported SAE or AESI on the BI SAE form via fax immediately (within 24 hours) to the sponsor's unique entry point (country specific contact details will be provided in the ISF). The same timeline applies if follow-up information becomes available. In specific occasions, the investigator could inform the sponsor upfront via telephone. This does not replace the requirement to complete and fax the BI SAE form.

With receipt of any further information to these events, a follow-up SAE form has to be provided. For follow-up information the same rules and timeline apply as for initial information. All AEs, including those persisting after individual patient's end of trial, must be followed up until they have resolved, have been assessed as "chronic" or "stable", or no further information can be obtained.

For further details specific to the AE reporting of this extension trial see [Section 5.2.6.2.1](#).

5.2.6.2.3 Pregnancy

In rare cases, pregnancy might occur in a clinical trial. Once a patient has been enrolled in the clinical trial and has taken trial medication, the investigator must report any drug exposure during pregnancy in a trial participant immediately (within 24 hours) by means of Part A of the Pregnancy Monitoring Form to the sponsor's unique entry point.

The outcome of the pregnancy associated with the drug exposure during pregnancy must be followed up and reported to the sponsor's unique entry point on the Pregnancy Monitoring Form for Clinical Studies (Part B).

[figure not shown]
The ISF will contain the Pregnancy Monitoring Form for Clinical Studies (Part A and B).

As pregnancy itself is not to be reported as an AE, in the absence of an accompanying SAE and/or AESI, only the Pregnancy Monitoring Form for Clinical Studies and not the SAE form is to be completed. If there is an SAE and/or AESI associated with the pregnancy an SAE form must be completed in addition.

5.6 APPROPRIATENESS OF MEASUREMENTS

All measurements performed during this trial are standard measurements in CD treatment trials and will be performed in order to monitor safety aspects or assess treatment response in an appropriate way.

Therefore, the appropriateness of all measurements applied in this trial is given.

6. INVESTIGATIONAL PLAN

6.1 VISIT SCHEDULE

All patients are to adhere to the visit schedule as specified in the [Flow Charts](#). Each visit date (with its window) up to EOT is to be counted from Day 1. If any of these visits has to be rescheduled, the date of subsequent visit should be calculated from Day 1. EOT refers to the last dose administration of spesolimab at week 336. Additional visits for the purpose of re-testing of laboratory parameters or AE monitoring may be included as deemed necessary by the investigator.

6.2 DETAILS OF TRIAL PROCEDURES AT SELECTED VISITS

Study procedures to be performed at each visit are listed in the relevant [Flow Chart](#) and the respective protocol sections. Refer to [Section 5](#) and [Section 10](#) (Appendices) for explanations of procedures. Additional details on procedures at selected visits are provided below.

6.2.1 Screening and run-in period(s)

Screening Period

After patients have been informed about the trial, written informed consent in accordance with GCP and the local legislation must be obtained prior to performing any study related procedures. Once they have consented, the patient is considered to be enrolled in the trial. The patient should be recorded on the patient enrolment log. Patient will be assigned a patient number and enrolment must be recorded in the eCRF pages.

Screening Visit (Visit 1):

Visit 1 should be performed in one visit, in combination with EOT visit of the preceding trial. Procedures performed at EOT visit of previous trial should not be repeated at V1 of 1368-0007. Visit 1 could be performed up to 28 days after EOT of preceding trial in exceptional cases. Procedures of V1 will not need to be repeated if investigator considers that patient do not have any clinical significant change.

At this visit, information will be collected for evaluation of trial eligibility as indicated in the [Flow Chart 1](#).

For more details regarding procedures at V1 please refer to [Flow Chart 1](#) or [Flow Chart 2](#).

Baseline Conditions

These are ongoing conditions with onset date prior trial inclusion. However, if these conditions are AEs of the parent trial and still ongoing after first dose in extension trial, they should not be recorded as baseline conditions. In such situations [section 5.2.6.2](#) should be followed.

Patients who have a laboratory test value outside the range specified by the eligibility criteria may have the test repeated to determine eligibility. The result must be available prior to Visit M1 (Day 1).

Demography

Informed consent date, gender, age, race and ethnic origin will be collected in the eCRF page. Also, the patient's smoking history will be assessed. Information concerning race/ethnicity will be collected, as it has been suggested that there may be race/ethnicity variations in the incidence, phenotypic manifestations, and outcome of CD. Note: In some countries, race may not be collected.

Medical and Surgical History

Information on clinically significant previous and concomitant diseases, other than CD, should be registered in baseline conditions as follow up from the parent induction studies.

Blood sampling

Blood samples will be drawn for safety lab, infection screening, [REDACTED]. Safety labs will be done at local lab only at this visit. There will be specific Central lab kits for parameters not checked at EOT of parent trial, as infection screening, HbA1C, THS, urine protein. From this visit, all labs will be done through the Central Lab Details will be provided in the laboratory manual and the ISF.

Pregnancy testing

For women of childbearing potential, a urine pregnancy test will be performed.

Infection screening

Infection testing will include tuberculosis, hepatitis B, hepatitis C, and HIV assessments (see [Table 5.2.3:1](#)).

Quantiferon TB testing

Patients with suspected false positive or indeterminate QuantiFERON TB result may have the test repeated once. If after repeat testing the QuantiFERON TB result is “indeterminate” a PPD skin test may be performed locally. A tuberculin skin test reaction $\geq 10\text{mm}$ ($\geq 5\text{mm}$ if receiving $\geq 15\text{mg/d}$ prednisone or its equivalent) is considered positive.

Patients who now test positive for QuantiFERON TB test may continue and receive treatment in this study if further work up (according to local practice/guidelines) establishes conclusively that the patient has no evidence of active tuberculosis.

If presence of latent tuberculosis is established, patients can receive anti-tuberculosis treatment (according to local practice/guidelines) and continue receiving study medication.

6.2.2 Treatment period(s)

The treatment period is lasting from Visit M1 until End of Treatment (EOT) Visit.

Study related procedures during treatment period will be performed as specified in the [Flow chart 1](#) and [Flowcharts 2](#), in case patients develop an inflammatory flare or fistula relapse.

Pregnancy testing

Urine pregnancy testing for all women of child-bearing potential will be conducted on-site every 4 weeks at visits with study drug administration and must be negative to continue

treatment. More frequent testing should be done if required by the local regulation and / or authority or per investigator judgment.

The pregnancy testing should be done **prior to** study drug administration. A positive urine test must be confirmed with a serum pregnancy test.

Blood sampling

Blood sampling (e.g., for safety lab, []) should be done, if applicable, **prior to** study drug administration and **prior to** rectoscopy/proctoscopy. It is not required that patient is fasted prior to collection of the safety laboratory testing as indicated in [Flowcharts](#), but patient has to be asked and information will be collected on lab requisition form if patient was fasting or not 8 hours prior to blood sampling.

Endoscopy (Proctoscopy/rectoscopy/sigmoidoscopy/ colonoscopy or full ileocolonoscopy). It will be performed once per year during treatment period. Additionally, ileocolonoscopies have to be done in case of disease flare as indicated in [Flowchart 2](#).

Ileocolonoscopy can be performed instead of proctoscopy or rectoscopy if required per local guidelines (i.e. colon cancer screening or others) or routine clinical practice.

Stool sampling

A stool sample will be collected for faecal biomarkers.

Clinical monitoring after study drug administration:

Local tolerability at the administration site of the subcutaneous injection will be assessed by the investigator at the specified visits as noted in the [Flow Chart](#).

At all dosing visits vital signs will be assessed pre- and post-dose, please see [section 5.2.2](#) for further details.

Unscheduled visits

The patient may be asked for additional unscheduled visits due to safety reason at the discretion of the investigator or the sponsor, unless the patient has withdrawn his/her consent. The patient may also contact the site due to safety reason for an unscheduled visit. The unscheduled visit may include additional collection of blood samples for safety reasons and

also additional assessments deemed necessary by the investigator such as laboratory samples, ECGs, or other procedures which were missed at a previous visit. All unscheduled visits should be described (including the reason for the visit) and documented in the medical/source record, and in the eCRF.

Concomitant medication review

Data concerning concomitant medications and procedures will be collected throughout the trial, as specified in the [Flow Charts](#). These data will be obtained at scheduled or unscheduled trial visits based on information provided spontaneously by the patient or as a result of questioning the patient.

